The conduct of the study will be monitored by representatives of Karl Storz ([name]) and the Global Coordinator ([name] and [name]) to ensure compliance with the protocol, GCP, ICH and applicable regulations. The coordinator will have regular contacts with the study centers, including remote access to provide information and support to the investigator(s) and confirm that the investigational team is adhering to the protocol, that data are being accurately and timely recorded in the RedCap.

The coordinator will perform source data verification (SDV) (a comparison of the data in the RedCap with the patient's medical records and other records relevant to the study including verification of informed consent of participating patients. This will require direct access to all original records for each patient (eg, clinic charts).

The Investigator must ensure that clinical study records are retained according to national regulations, as documented in the clinical trial agreement entered into with the Sponsor in connection with this study. Subject files and other source data must be kept for the maximum period of time permitted by the hospital, institution, or private practice. The Investigator must inform The Main Center (Cleveland clinic Florida) immediately if any documents are to be destroyed, to be transferred to a different facility, or to be transferred to a different owner.

The co- investigators will permit study-related monitoring, audits, and inspections by the IRB, the sponsor, government regulatory bodies, and

Institutional compliance and quality assurance groups of all study related documents (for example, source documents, regulatory documents, data collection instruments, study data etc.). Participation as an investigator in this study implies acceptance of potential inspection by government regulatory authorities and applicable Institutional compliance and quality assurance offices.”

18. Publication Plan

The parties, recognizing the importance of communicating clinical trial results to the public and to the medical and scientific communities in an accurate and complete manner, intend for the first Publication of the Study to include the results from all of the study centers and to appear in a peer-reviewed scientific journal, in accordance with the Protocol.

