h. Schedule of events	45
i. WMA Declaration of Helsinki - Ethical Principles for Medical Research Involving Human Subjects.....	46
i. Preamble.....	46
ii. General Principals	46
iii. Risks, Burdens and Benefits.....	47
iv. Vulnerable Groups and Individuals.....	48
v. Scientific Requirements and Research Protocols	48
vi. Research Ethics Committees	49
vii. Privacy and Confidentiality	49
viii. Informed Consent.....	49
ix. Use of Placebo.....	50
x. Post-Trial Provisions.....	51
xi. Research Registration and Publication and Dissemination of Results	51
xii. Unproven Interventions in Clinical Practice	51

1. Summary

Title:	Efficacy of Near Infrared Incisionless Fluorescent Cholangiography (NIFC) during Laparoscopic Cholecystectomy (LC)
Primary Objective:	Demonstrate that NIFC performs better than standard white light (WLI) alone in visualizing and identifying extra-hepatobiliary structures (Cystic Duct, Right Hepatic Duct, Common Hepatic Duct, Common Bile Duct, Cystic-CBD junction, Cystic-Gallbladder junction, and any Accessory Ducts) before and after dissection during Laparoscopic Cholecystectomy (LC).
Secondary Objectives:	
1. Demonstrate that NIFC is an effective teaching tool to assist students and residents present in the O.R. during the procedure to identify extra-hepatobiliary structures (before/after dissection).2. Demonstrate that the Time to Clip, which is defined as the time from the moment Calot's Triangle is first visualized to when the clip is applied, is reduced when using NIFC vs WLI alone.3. Compare the mean number of procedures that required Conversion to Open using NIFC vs WLI alone.4. Compare the mean Volume of Bleeding using NIFC vs WLI alone.5. Compare the Incidence rate of Bile Leakage from the liver bed using NIFC vs WLI alone.6. Compare the Incidence rate of Bile Duct Injury (BDI) using NIFC vs WLI alone.7. Compare the mean Surgeon Confidence Level using NIFC vs WLI alone.
Indication:	Laparoscopic Cholecystectomy (LC)
Investigational Design:	Two arms multi-center randomized controlled clinical trial with patients randomized by center.
Inclusion/exclusion criteria:	
Inclusion Criteria
 
1. Patients of both genders2. Minimum age: 18 years old3. Spoken and written command of the language spoken in the country's center

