	
4. Ability to understand and follow the study procedures and sign the informed consent
 
Exclusion Criteria
 
1. Known allergies to iodides2. Known history of cholangitis, pancreatitis, CBDS's, coagulopathy3. Known liver disease4. Women who are pregnant or breastfeeding, or for whom possibility of pregnancy was not ruled out 
1,000 patients enrolled across all centers
 
Male or female subjects undergoing laparoscopic cholecystectomy that fulfil all of the inclusion and none of the exclusion criteria.
 
Approximately 1 year
 
Primary Endpoints:
 
Detection Rate (DR) of each particular extra-hepatobiliary structure during Laparoscopic Cholecystectomy (LC) defined as the total number of patients in which the particular structure is detected before and after dissection in that arm of the Study (WLI or NIFC), divided by the total number of patients in that arm. Extra-hepatobiliary structures to be included in this assessment: Cystic Duct, Right Hepatic Duct, Common Hepatic Duct, Common Bile Duct, Cystic-CBD junction, Cystic-Gallbladder junction, and any Accessory Ducts.
 
Secondary Endpoints:
 
1. The DR for students/residents only (apart from experienced surgeons), both before and after dissection.2. Time to Clip3. Incidence of Conversion to Open Surgery4. Volume of Bleeding5. Incidence of Bile Leakage from the liver bed6. Incidence of Bile Duct Injury (BDI)7. Surgeon Confidence Level 
Test Device/Procedure:
 
Image1 SPIES (Storz Professional Image Enhancement System) Endoscopic ICG Imaging System
 
Comparator Device/Procedure:
 
Standard Image1 SPIES Endoscopic System using white light imaging (WLI) only
 
Statistical Analysis:
 
The DR (before and after dissection) between arms will be compared using the chi-square test while the number of

--	--

structures detected will be analyzed using non-parametric tests. Regression models (logistic or generalized mixed models) will be fitted to evaluate if the effect of NIFC on the primary outcomes is modified by the patient's or surgeon's characteristics or the site.

2. Introduction

a. Background

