Upon entry in the clinical trial, the master study database (REDCap, described later in Section 16) will randomly allocated patients to one of the study arms (1:1) within site (1:1) using a computer generated random sequence. This will provide an allocation sequence for each site. Once a patient is enrolled and a database file in REDCap is initiated for that patient, he/she will be assigned electronically to one of the study arms.

Patient will be blind to the intervention but surgeon blinding will not be feasible due to the nature of the intervention. The study will involve a considerable number of surgeons in each site, which should compensate any potential bias of some of them in favor or against either approach.

e. Flow chart

Multi-center Study Protocol: Efficacy of Near Infrared Incisionless Fluorescent Cholangiography (NIFC) during Laparoscopic Cholecystectomy

[figure not shown]
Figure 1 shows the flow chart for the study, a multi-centered randomized controlled trial (RCT) 1:1 with two arms:

1. Control: WLI

A laparoscopic cholecystectomy will be performed using Xenon white light imaging (WLI) only.

2. Experimental: NIFC

A laparoscopic cholecystectomy will be performed using both white light imaging and near infrared light imaging with indocyanine green (ICG) intravenous dye.

9. Data collection and procedures

Data will be collected before, during and at the end of surgery; and one week after surgery.

a. Pre-Op data collection

i. Patient data

- Age
- Gender
- Weight
- Height
- BMI

ii. Patient clinical characteristics

- Liver disease
- Lithiasis
- Surgical status: elective/urgent/emergent

b. Intra-Op data collection

i. For NIFC arm only

- Time of ICC administration
- Was there any Adverse Reaction? If so, what happened and how was the patient treated?

ii. For both arms: PRIOR to dissection

- Categorize initial visualization
 - Amount of fat
 - Amount of inflammation
 - Presence of adhesions / scar tissue
- Remove the fat from the Calot's triangle area, retract the gallbladder and Hartmann's pouch
- Surgeon/Observer documents which extra-hepatic biliary structures are identified without doubt
- Start Dissection. Document the time hilar dissection was begun (baseline time)

iii. For both arms: AFTER dissection

- Surgeon/Observer documents which extra-hepatic biliary structures are identified without doubt
- Time to Clip: Document the time the Cystic Duct was clipped
- Volume of Bleeding
- Incidence of Bile Leakage

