Regarding the main secondary outcome, incidence of injuries, the power to detect a drop from 8/1000 in the control arm to 2/1000 in the intervention arm, with a sample size of 500 patients per arm is 15%. Regretfully, with an achievable sample size as the one proposed above, the study will not have enough power to detect a drop in the incidence as important as the one considered.

b. Data Analysis

In general, descriptive statistics including frequencies and means will be used to characterize patient's baseline characteristics in both study arms. Analyses are designed to test the following hypotheses based on the primary objectives: Compared to those in the control arm, surgeons using NIFC will be able to identify a) more frequently the gallbladder cystic union (both before dissection and before clipping); b) a larger number of hepato-biliary structures and; c) more frequently some of the five hepato-biliary structures. We will test the first hypothesis using the chi-square test, the second one using non-parametric test (e.g. Kruskal-Wallis) and the third one using generalized mixed or hierarchical models to account for the clustering induced by the patient.

Multi-center Study Protocol: Efficacy of Near Infrared Incisionless Fluorescent Cholangiography (NIFC) during Laparoscopic Cholecystectomy

Regression models (logistic or generalized mixed models) will be fitted including covariates to evaluate if the effect of NIFC on the primary outcomes is modified by the patient's or surgeon's characteristics and site.

Regarding secondary outcomes we will use the Fisher's exact test or Chi square test (as needed) to compare proportion of patients with bile duct injury, open surgery or bleeding. Time to clipping and time to end of surgery will be compared between arms using the Kruskal-Wallis' test. Regression models will be used when possible -we expect very low incidence of injuries and open surgeries- to evaluate patient's and surgeon's effect modification.

Finally, for those outcomes specific for the NIFC group we will use logistic or generalized linear models to assess whether the reported helpfulness of the NIR light or the reflux maneuver is associated to patient's characteristics or surgeon's experience.

All statistical analysis will be conducted in R software.

14. Anticipated Problems and Solutions

a. Lower than expected Enrollment

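### Patients are randomized within site, but the primary tests do not use site: they are valid as planned, and stratifying them by site is a small improvement at no cost in patients or data

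*Combined protocol and SAP*

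**What the plan says.** The Summary describes the trial as "Two arms multi-center randomized controlled clinical trial with patients randomized by center". Section 8.d gives the mechanism: REDCap assigns each patient "to one of the study arms (1:1) within site (1:1) using a computer generated random sequence", so every site has its own allocation sequence. Blocking is not mentioned.

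None of the primary between-arm tests names site:

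- Detection rate (DR): the Summary states that "The DR (before and after dissection) between arms will be compared using the chi-square test". Section 13.b says "We will test the first hypothesis using the chi-square test", where that hypothesis is detecting "more frequently the gallbladder cystic union (both before dissection and before clipping").
- Number of structures: "the second one using non-parametric test (e.g. Kruskal-Wallis").
- Individual structures, hypothesis (c): a comparison "using generalized mixed or hierarchical models to account for the clustering induced by the patient". The patient is the only clustering named.

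Site does enter the plan elsewhere. The Summary and section 13.b both fit regressions asking whether the NIFC effect "is modified by the patient's or surgeon's characteristics and site". Section 13.a plans on six centers, and section 8.b lists nine.

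**The concern.** When allocation is stratified by site, the natural primary comparison is also made within site. Pooling all patients into one two-by-two table leaves the differences between sites in the error term. The protocol itself gives reasons to expect such differences: section 2.c points to varied patients and surgeons across continents, and section 12.c has each surgeon follow the center's own surgical routine. The effect-modification regressions do not fill the gap, because they ask whether the effect varies and not whether there is one.

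What is at stake is some power, and possibly a test that runs below its nominal level. The truth of a positive result is not in doubt on this account.

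**Working it through.** **Inputs from the documents.** 1,000 patients, 500 per arm (Summary, 13.a, 13.b); one-sided 5% and a target of 90% power or more (13.a); cystic-gallbladder junction 60% + 9 points before dissection and 70% + 8 points after (13.a table); six or nine sites.

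**Assumed, because the documents give no figure.** Normal site effects on the logit scale with SD 0, 0.5 or 1.0. With a median site rate of 70%, the central 95% of sites would span 47-86% at SD 0.5 and 25-94% at SD 1.0. SD 1.0 is best read as an upper bound, since section 8.b describes all sites as recognized specialist centers.

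**Step 1: reproduce the plan's table.** Pooled two-proportion power, no continuity correction, no site term:

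power = Φ[(d − 1.645·√(2p̄(1−p̄)/n)) / √((p0(1−p0)+p1(1−p1))/n)]

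- 70 vs 78%: p̄ = 0.74, so (0.08 − 1.645 × 0.02774) / 0.02763 = 1.244 and power = 0.893.
- 60 vs 69%: p̄ = 0.645, so (0.09 − 1.645 × 0.03026) / 0.03013 = 1.335 and power = 0.909.

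All 13 cells give 0.893 to 0.944. The table therefore reproduces as an unstratified one-sided test. Its weakest cells (70% + 8) fall just under the stated 90%.

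**Step 2: what each test does with site.** The pooled variance p̄(1−p̄) equals the average within-site variance plus the variance of the site rates. The chi-square keeps both parts. The signed CMH statistic keeps only the first:

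Z = Σ(x1k − n1k·mk/Nk) / √Σ[n1k·n0k·mk(Nk−mk) / (Nk²(Nk−1))]

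Here k is the site, n1k and n0k are the arm sizes, x1k is the number detected in the NIFC arm, mk is the number detected in both arms, and Nk is the site total. If allocation is unblocked, the between-site part is real noise, so the chi-square is correct but less efficient. If allocation is blocked, that part cancels between arms and the chi-square overstates its error. A rough check at 70%, SD 0.5: site variance ≈ (0.7 × 0.3 × 0.5)² = 0.0110, or 5.25% of 0.21. The actual level is then 1 − Φ(1.645/√0.9475) = 1 − Φ(1.690) ≈ 4.6%.

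**Step 3: simulated error of the chi-square, nominal 5%.** Unblocked: 4.8-5.2%. Blocked: 4.5-4.8% at SD 0.5 and 3.7-3.9% at SD 1.0. It does not exceed 5% beyond simulation noise.

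**Step 4: simulated power.** Equal sites, 40,000 trials per scenario, marginal rates held at the table values. Each cell gives six / nine sites.

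| DR | SD | Within site | Chi-square | CMH |
|---|---|---|---|---|
| 70 vs 78% | 0.5 | unblocked | 0.893 / 0.892 | 0.901 / 0.900 |
| 70 vs 78% | 0.5 | blocked | 0.898 / 0.897 | 0.903 / 0.903 |
| 70 vs 78% | 1.0 | unblocked | 0.889 / 0.893 | 0.922 / 0.926 |
| 70 vs 78% | 1.0 | blocked | 0.905 / 0.906 | 0.922 / 0.927 |
| 60 vs 69% | 0.5 | unblocked | 0.911 / 0.909 | 0.919 / 0.918 |
| 60 vs 69% | 0.5 | blocked | 0.915 / 0.914 | 0.921 / 0.920 |
| 60 vs 69% | 1.0 | unblocked | 0.909 / 0.906 | 0.944 / 0.942 |
| 60 vs 69% | 1.0 | blocked | 0.923 / 0.927 | 0.943 / 0.946 |

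The gains here are 0.5-0.9 points at SD 0.5 and 1.7-3.6 at SD 1.0. Separate runs gave up to 1.1 points at SD 0.5. At SD 1.0 they gave about 1.5 points with unequal blocked sites (0.9250 to 0.9397), and just under 4 when the site rates spanned 23-90% (0.9070 to 0.9465). With identical sites, CMH loses up to about 0.2 points in most runs and 0.35 at worst.

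In patients: 1000 × [((1.645 + z_CMH)/(1.645 + z_chi))² − 1], with z the normal quantile of each power. For 0.893 vs 0.901 this is 1000 × [((1.645 + 1.287)/(1.645 + 1.243))² − 1] ≈ 31.

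**Step 5: where the gain disappears.** At SD 1.0, accessory ducts before dissection (1% + 3) and common bile duct after (96% + 3) gain 0.3 points or less. For the number of structures, both rank tests have 99.9% power or more at the full tabulated increases. At half those increases, with an assumed patient logit SD of 1.0, the van Elteren test gains 1.5-3.6 points at SD 0.5 if a site's effect is shared by all structures, and −0.2 to 0.4 if it is independent by structure. The gain from adding site to the mixed model was not simulated.

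**The case against.** The best case against the point is that it is optional. The tests are valid, the gain at moderate site differences is about one point, and the documents give no between-site figure to support more. The cystic-gallbladder junction is also among the rows that gain most. All of that stands and is built into the size stated below. It is also fair that the plan is looser than a bare list of tests suggests: Kruskal-Wallis is only an example, and a mixed or hierarchical model can carry a site term. The wording permits stratification without committing to it, so naming it in advance still has value.

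A reader might infer three stronger things that the documents do not support:

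- From "Two arms multi-center randomized controlled clinical trial with patients randomized by center", that whole centers were randomized, which would make a patient-level chi-square invalid. Section 8.d rules this out: individual patients are allocated 1:1 inside each site.
- That ignoring site inflates false positives. It does not under either form of allocation (step 3).
- That the plan overlooks site altogether. It has the effect-modification regressions.

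The Mantel-Haenszel risk difference is a site-weighted summary and not the simple difference of the arm rates that define the endpoint. That is a reason to report both.

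**Conclusion.** The point holds as an improvement worth making, not as an error. The unstratified tests keep their level or fall below it, and the sample-size table stands as a one-sided calculation, apart from its lowest cells at 89.3%. For mid-range detection rates, stratifying costs up to about 0.2-0.35 points of power if sites are alike, gains about 0.5-1 point at logit SD 0.5, and gains about 1.5-3.6 points at SD 1.0. The gain is essentially nil for accessory ducts, for the common bile duct after dissection, and for the number of structures at the tabulated increases. These sizes rest on assumed site spreads; the direction does not. Six or nine sites give similar results.

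Two neighboring questions are separate and do not add weight here: which test governs the structures other than the gallbladder-cystic junction, and whether a two-sided level was intended.

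**What to change.** In the Summary and section 13.b:

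- Wherever the chi-square is named, use a signed CMH test stratified by the sites that have their own REDCap sequence.
- Report the Mantel-Haenszel risk difference with a 95% confidence interval, using weights n1k·n0k/Nk, beside the crude arm rates.
- Name the van Elteren test, stratified by site, for the number of structures.
- Add site to the mixed model for hypothesis (c), leaving that model's role unchanged.
- Keep the one-sided 5% level of section 13.a.
- Reconcile the six centers of 13.a with the nine of 8.b so that the strata are defined, and state whether the sequences are blocked.

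The cost is text only. Institution is already on the case report forms, so no patient, visit or variable is added, and the sample-size table does not change. The wording should be settled before outcome data by arm are seen.
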